8.7.2 Analysis of Secondary Efficacy Variables

All analysis on secondary efficacy variables will be performed using FAS.

The secondary efficacy endpoint is to evaluate the change in FPG from baseline to week 24 of MP-513 compared to Placebo. The same statistical methodology as described for primary analysis on primary efficacy endpoint will be used.

The line graph for mean change in FPG from baseline to Week 24 and Week 24 (LOCF) will be presented. The 95% CIs will also be shown in the graph with error bar. The plots of Week 24 and Week 24 (LOCF) will not be connected.

8.7.3 Analysis of Other Efficacy Variables

All other efficacy endpoint will be analysed using FAS. The other efficacy endpoints are as follows:

- Proportion of subjects who achieved HbA1c < 7.0% at Week 24
- Change in fasting insulin, C-peptide, and glucagon from baseline to Week 24
- Change in HOMA-IR and HOMA-β from baseline to Week 24
- Change in body weight from baseline to Week 24
- Change in HbA1c and FPG from baseline to Week 12

Proportion of subjects who achieved HbA1c < 7.0% at Week 24 (LOCF):

For the proportion of subjects who achieved HbA1c < 7.0% at Week 24 (LOCF), the comparison between treatments will be performed using logistic regression with treatment as fixed effect and baseline HbA1c value as a covariate. The subjects who have HbA1c < 7.0% at baseline will be excluded from the analysis.

The odds ratio (OR) with 95% Wald CIs will be presented for between treatment groups comparison of responder rate (i.e. proportion of subjects who achieved HbA1c < 7.0% at Week 24). The Wald Chi-Square p-value for significance of treatment effect after controlling for baseline HbA1c will also be displayed.

For logistic regression analysis, the dichotomous response variable will be coded as '1' (for subjects who achieved HbA1c < 7.0% at Week 24) and '0' for subjects for whom HbA1c ≥ 7.0% at week 24.

The frequency count and percentage of subjects who achieved HbA1c < 7.0% at week 24 will also be summarized by treatment groups.

Other efficacy endpoints:

For the remaining other efficacy endpoints, namely;

- Change in fasting insulin, C-peptide, and glucagon from baseline to Week 24
- Change in HOMA-IR and HOMA-β from baseline to Week 24
- Change in body weight from baseline to Week 24
- Change in HbA1c and FPG from baseline to Week 12

The line graph for mean change in other efficacy endpoints from baseline to Week 24 and Week 24 (LOCF) will be presented. The 95% CIs will also be shown in the graph with error bar. The plots of Week 24 and Week 24 (LOCF) will not be connected.

The same statistical methodology as described for primary analysis on primary efficacy endpoint will be used.

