1.2. Protocol Synopsis

Sponsor: Mitsubishi Tanabe Pharma Corporation	Name of Medical Product: MP-513	Active Ingredient(s): Teneligliptin
Study Centre(s): Multi-centre study that will be conducted in approximately 35 sites in China		
Study Duration: 30 weeks (2 weeks screening, 2 weeks placebo run-in, 24 weeks treatment, 2 weeks follow-up) The study period is estimated to start from [REDACTED] to [REDACTED].		Study Phase: 3
Study Title: A phase 3 randomized, double-blind, placebo-controlled parallel group efficacy and safety monotherapy study of MP-513 in Chinese subjects with type 2 diabetes mellitus inadequately controlled with diet and exercise		
Study objectives: To evaluate the efficacy and safety of MP-513 compared with placebo in Chinese subjects with type 2 diabetes mellitus inadequately controlled with diet and exercise		
Methodology: Multi-centre, randomized, double-blind, placebo-controlled, parallel-group study		
Number of Subjects (Planned): 240 subjects (120 subjects to MP-513 and 120 subjects to placebo)		
Diagnosis and Inclusion Criteria: The subjects have to meet all of the following inclusion criteria: 
 1. A signed and dated informed consent form has been obtained from the subject, in accordance with International Conference on Harmonisation guidelines on Good Clinical Practice (ICH GCP), before any screening or study related procedures take place. 2. The subject is aged ≥ 18 years at signature of the informed consent form 3. Hospitalization status: outpatient 4. The subject has had a documented diagnosis of type 2 diabetes mellitus for at least 3 months at the screening visit (Day -28) 5. The subject is undergoing diet and exercise therapy, and diet and exercise regimen has not been changed for at least 8 consecutive weeks at the screening visit (Day -28). Subjects who cannot do exercise due to complication are not limited to this criteria. 6. The subject's glycosylated fraction of haemoglobin (HbA1c) is $\geq 7.0\%$ and $< 10.0\%$ at the screening visit (Day -28) and on Day -14. 7. The subject's fasting plasma glucose (FPG) is < 270 mg/dL (15 mmol/L) at the screening visit (Day -28) and on Day -14. 8. The subject is capable of giving informed consent, complying with the restrictions and requirements of the protocol and, in the opinion of the investigator, will be able to complete the study. 		

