6.4.2 Method of Assigning Subjects to Treatment Groups

Subjects will be randomized to MP-513 or placebo in a 1:1 ratio according to a computer-generated randomization code.

Treatment assignment will be managed through static blocked randomization and an Interactive Web Randomization System (IWRS) will be used.

The randomization scheme will be reproducible and will be prepared by the CRO via a computerized system prior to start of the study. Separate lists will be prepared for subjects' randomization (randomization code list) and study medication packaging (kit code list).

The IWRS provider will retain master copies of the randomization and kit code list (in a secure fashion in order to maintain the blind).

At the randomization visit (Day 1), after confirmation of subject eligibility, the Investigator will connect to the randomization system in order to receive kit number containing the study treatment, then subjects will receive the double-blinded study treatment which is assigned to them.

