6.4.4 Blinding

Study treatments will be packaged for double-blind administration. The placebo is identical to the corresponding active treatments. During the single-blind run-in period, the subject will not know that they are receiving placebo. During the double-blind treatment period the subject, the investigator, the laboratory personnel, and the sponsor other than a designated person would not know the treatment arm to which a subject is assigned.

Only the IWRS provider will know the treatment arm that each individual subject is randomized to.

The investigators are strongly discouraged from requesting the blind be broken for an individual subject, unless there is a subject safety issue that requires unblinding and knowledge of the treatment group would change subject management. If the blind is broken by the Investigator, the date, time and reason must be recorded in source document and subject's eCRF and the relevant subject will discontinue the study. The unblinding procedure is described in detail in the IWRS instruction manual that will be provided separately to the Investigator.

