6.9.1.1 General Considerations

All significance tests will be carried out at a 5%, 2-sided significance level. Statistical tests will be supported by presenting estimates and 95% confidence intervals for the respective treatment effects and differences between the treatment groups. These estimates, confidence intervals and p-value will be based on the respective statistical models used for the analysis.

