6.2.2 Windows

For the purpose of effectiveness and safety analysis, all scheduled and unscheduled clinic visits will be windowed as presented in the below table. The planned protocol visit window will be used for analysis.

Table 3 Schedule of Visits

Visit	Week	Scheduled Study Day	Visit Window in Protocol (Days)
Randomization Visit (RV)	Randomization Visit (RV)	1	1
Visit 1	Week 4	28	21 – 35
Visit 2	Week 8	56	49 – 63
Visit 3	Week 12	84	77 – 91
Visit 4	Week 16	112	105 – 119
Visit 5	Week 20	140	133 – 147
Visit 6	Week 24	168	161 – 175
Follow-up Visit	Week 26	182	182 – 196

If a visit day is outside of these windows, then it is considered as non-windowed, otherwise it is windowed. If a subject has more than one assessment occurring in the same visit window, the data from the visit closest to the scheduled study day will be used. If two visits have the same distance from the scheduled study day, the data of the visit after the scheduled study day will be used.

The unscheduled visits will be chronologically arranged between two scheduled visits. The unscheduled visits will be numbered sequentially with an increment of 0.1 to the visit number corresponding to scheduled visit preceding the unscheduled visit. For example, if two unscheduled visits occur between visit 1 (visit number is 10) and visit 2 (visit number is 20), then these unscheduled visits will be numbered 10.1, 10.2 in the order they occurred.

The assessments made in unscheduled visits will be considered in imputation of missing assessment using Last Observation Carry Forward (LOCF) method for Week 12 or Week 24.

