7.3 Handling of Dropouts or Missing Data

Subjects who discontinue the study prior to or after the initiation of the study drug will not be replaced and available data of these subjects until the point of discontinuation will be summarized. The missing baseline assessment will not be imputed.

For categorical variables with missing values, a category documenting the frequency of missing values will be displayed in the summary tables.

The missing HbA1c and FPG value at week 12 or week 24 will be imputed using last observation carried forward (LOCF) approach. Baseline value will not be used to impute missing data. The missing data of Fasting insulin, C-peptide, Glucagon, HOMA-IR, HOMA- β and Body weight at week 24 will also be imputed using LOCF approach.

The supportive analysis for primary efficacy will be done using observed values.

There will be no imputation of missing values in database of safety data, however missing relationship between AE and study medication will be considered as related to treatment following worst case principle. Missing severity of an AE will be summarized as severe AE.

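### LOCF can credit early stoppers with reaching HbA1c < 7.0% at Week 24, and no second analysis of that endpoint is planned

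*SAP*

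**What the plan says.** The endpoint is listed in SAP 8.7.3 among the other efficacy endpoints, below the primary and secondary ones: "Proportion of subjects who achieved HbA1c < 7.0% at Week 24". It is analysed on the FAS: "For the proportion of subjects who achieved HbA1c < 7.0% at Week 24 (LOCF), the comparison between treatments will be performed using logistic regression". The model contains treatment and baseline HbA1c. The response is 1 below 7.0% and 0 otherwise. Whether the subject was still in the study plays no part in the coding.

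The imputation rule is in SAP 7.3: "The missing HbA1c and FPG value at week 12 or week 24 will be imputed using last observation carried forward (LOCF) approach". Baseline is never carried forward. SAP 6.2.2 widens the source of the carried value: "The assessments made in unscheduled visits will be considered in imputation of missing assessment using Last Observation Carry Forward (LOCF) method". Protocol 6.9.1.2 also specifies LOCF for efficacy values missing at Week 12 and Week 24, so the two documents agree.

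Stopping ends HbA1c collection. Protocol 6.3.3 treats adverse events, deterioration, withdrawn consent, investigator decision and lack of glycaemic control as reasons to leave the study. After unblinding by the investigator, "the relevant subject will discontinue the study" (Protocol 6.4.4). Protocol 6.6.1 places the early termination visit, which includes HbA1c, within 7 days of the decision to discontinue. The only later contact is by telephone.

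The two supportive analyses in SAP 8.7.1.2 (the PPS analysis and the MMRM) concern mean change in HbA1c. None is given for the responder endpoint.

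**The concern.** The endpoint is worded as a status reached at Week 24. Under LOCF, a subject who stopped MP-513 at Week 8 with an HbA1c of 6.9% is reported as on target at Week 24, 16 weeks after leaving. No true Week 24 value exists for that subject, and the plan has no analysis that treats such subjects differently.

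If the drug works, a larger share of MP-513 dropouts than of placebo dropouts will have a last value below 7.0%. The carried-forward successes then need not cancel between the arms. At stake are the two responder rates, which readers tend to take literally, and the difference, odds ratio and p-value built on them.

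**Working it through.** **1. What the documents supply.** The plan is for "240 subjects (120 subjects to MP-513 and 120 subjects to placebo"), allocated 1:1, with two-sided tests at 5%. The sample-size sections are redacted, and the visible text gives neither an expected responder rate nor a dropout rate. There is no figure of the plan's own to reproduce here, and every rate below is an assumption.

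**2. Formula.** In each arm let r be the completers' responder rate, d the dropout proportion, and c the share of dropouts whose last value is below 7.0%.

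- LOCF rate = (1 − d)·r + d·c
- Non-responder rate (discontinued = 0) = (1 − d)·r
- LOCF minus non-responder, in the between-arm difference = dT·cT − dC·cC

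**3. Arithmetic with r = 40% (MP-513) and 20% (placebo), and c = r.** LOCF then gives 40% v 20% throughout: 20.0 points, OR (0.40/0.60)/(0.20/0.80) = 2.67.

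| Dropout MP-513 / placebo | Non-responder rates | Difference | OR | LOCF excess |
|---|---|---|---|---|
| 5% / 5% | 38% v 19% | 19.0 | 2.61 | 1.0 |
| 10% / 10% | 36% v 18% | 18.0 | 2.56 | 2.0 |
| 20% / 20% | 32% v 16% | 16.0 | 2.47 | 4.0 |
| 20% / 10% | 32% v 18% | 14.0 | 2.14 | 6.0 |
| 10% / 20% | 36% v 16% | 20.0 | 2.95 | 0.0 |

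In the last row the excess vanishes on the difference scale, and LOCF gives the smaller odds ratio.

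**4. Simulation A** (400,000 per arm). Baseline mean 8.0%, SD 0.8, limited to 7.0–10.0%. Effect −0.75, close to the −0.79 at Week 12 in the Japanese placebo-controlled study 3000-A5 (Protocol section 4), reached gradually. Equal non-glycaemic dropout, spread evenly over Weeks 4 to 20. About 31% of MP-513 dropouts and 7–8% of placebo dropouts carry a value below 7.0%.

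| Dropout per arm | LOCF difference | Non-responder difference | Excess |
|---|---|---|---|
| 5% | 28.2 | 27.0 | 1.2 |
| 10% | 27.9 | 25.5 | 2.4 |
| 15% | 27.5 | 24.0 | 3.5 |
| 20% | 27.2 | 22.5 | 4.7 |

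At 10% the rates are 36.7% v 8.8% (LOCF) and 33.6% v 8.0% (non-responder). The crude ORs are (0.367/0.633)/(0.088/0.912) = 6.01 and (0.336/0.664)/(0.080/0.920) = 5.82.

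**5. Simulation B** (400,000 per arm). Baseline mean 7.9%, SD 0.7, limited to 7.0–10.0%. Effects 0.48 (20 mg at Week 24 in study MP-513-E07) and 0.79. Random dropout, plus a stop above HbA1c 9.8% standing in for the FPG rule. Entries are the difference in points, with the crude OR in brackets.

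| Effect; random dropout MP-513 / placebo | All stayed on treatment | LOCF | Non-responder | Stoppers lose drug effect |
|---|---|---|---|---|
| 0.48; 10% / 10% | 17.7 (2.53) | 17.4 (2.52) | 16.0 (2.46) | 16.0 (2.34) |
| 0.79; 10% / 10% | 31.1 (4.38) | 30.5 (4.30) | 28.0 (4.07) | 28.0 (3.86) |
| 0.79; 20% / 20% | 31.1 (4.39) | 30.1 (4.26) | 24.9 (3.84) | 24.9 (3.41) |
| 0.48; 10% / 20% | 17.9 (2.54) | 17.7 (2.56) | 17.9 (2.83) | 16.0 (2.35) |

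**6. In subjects.** With 120 per arm, 10% dropout is 12 subjects. Simulation A's shares give 12 × 0.31 = 3.7 carried responders on MP-513 and 12 × 0.08 = 1.0 on placebo, a net of under 3. The standard error of the 10% LOCF difference is √(0.367×0.633/120 + 0.088×0.912/120) = 0.051, or 5.1 points. The 2.4-point excess is about half of that.

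**7. How firm the range is.** It depends on the carried shares. With r = 40% v 20%, 20% dropout per arm, cT = 0.40 and cC = 0.05, the excess is 0.20×0.40 − 0.20×0.05 = 7.0 points (OR 3.25 v 2.47). So 1 to 5 points is what the simulated trajectories give and is not a bound.

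**The case against.** A reader might infer that everyone who leaves between Week 4 and Week 20 is counted as on target. The coding does not do that. A last value of 7.0% or above gives 0, and with no post-baseline HbA1c there is nothing to carry. In simulation A about 69% of MP-513 dropouts and 92–93% of placebo dropouts are non-responders under LOCF too. Subjects removed under the FPG rule will mostly fall in that group.

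A reader might also infer that LOCF always inflates the MP-513 advantage. The documents do not show this. In simulation A the LOCF difference falls as equal dropout rises, from 28.2 to 27.2 points. The excess arises because the non-responder difference falls faster. LOCF also sits slightly below the result expected had everyone stayed on treatment, so inflation is relative to non-responder coding or to an off-drug outcome. The documents do not say which quantity is wanted. If random dropout is 10% on MP-513 and 20% on placebo, the comparison with non-responder coding reverses for the smaller effect (17.7 v 17.9 points; OR 2.56 v 2.83).

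Other mitigating facts stand. LOCF is prespecified in both documents and openly labelled. The early termination HbA1c is normally close to the end of treatment. Discontinuations are tabulated by arm (SAP 8.1) and all HbA1c values are listed (SAP 8.7), so a determined reader could reconstruct the carried responders.

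These arguments limit the size and direction of the problem without removing it. The reported Week 24 status is unobserved for early stoppers, and a listing does not replace a planned analysis. Higher placebo dropout through the FPG rule alone would do little to reverse the direction, because those subjects are mostly coded 0 under both rules. Reversal needs substantially more non-glycaemic dropout on placebo.

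**Conclusion.** The point holds in limited form. Early stoppers whose last post-baseline HbA1c is below 7.0% count as Week 24 responders, and no other analysis of this endpoint is planned.

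Under equal dropout of 5% to 20% per arm, the simulated excess over non-responder coding is about 1 to 5 points towards MP-513. The crude odds ratio changes little at 10% dropout and somewhat more at 20% with the larger effect. More dropout on MP-513 enlarges the excess. Substantially more non-glycaemic dropout on placebo can remove or reverse it.

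All of this rests on assumed dropout, carried shares and trajectories, and the odds ratios are crude whereas the planned one is adjusted for baseline. The primary and secondary endpoints are not touched by this point. Severity is low to moderate.

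**What to change.** In SAP 8.7.3, keep the protocol-specified LOCF analysis and place beside it a second logistic regression and frequency table in which subjects who discontinued before the Week 24 window (Days 161–175 in SAP 6.2.2) are coded 0. State how two small groups are handled: subjects who completed but lack a Week 24 HbA1c, and FAS subjects with no post-baseline HbA1c. Report by arm how many LOCF responders are carried-forward values.

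While editing, reconcile the baseline exclusion for this endpoint so that both analyses share a denominator. Protocol 6.9.1.5 excludes baseline HbA1c of 7.0% or below, whereas SAP 8.7.3 excludes only values below 7.0%.

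The cost is one derived variable and one extra table, with no new data. The added rule is conservative for subjects who left for reasons unrelated to treatment, which is why it should stand beside LOCF and be read with it.

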8.7.4 Subgroup Analyses

The sub-group analysis will be performed for the primary efficacy endpoint i.e. Change in HbA1c from baseline to Week 24 for the subgroups mentioned in section 7.10.

Analyses of these subgroups will be performed using FAS. The analysis will be based on the same methods described for the primary analysis of primary efficacy endpoint.

8.8 Analysis of Safety

All safety data will be summarized by treatment groups using the Safety Analysis Set. No formal statistical test would be performed to determine statistical significance between treatment groups.

8.8.1 Adverse Events

All AE summary tables will include only TEAEs, unless otherwise specified.

Adverse events will be summarized by SOC and PT. A subject will only be counted once per SOC and PT within a treatment.

For AEs by severity grade (mild, moderate, severe), if a subject has multiple events occurring in the same SOC or same PT, then the event with the maximum intensity (i.e. severe) will be counted.

For AEs by relationship to study drug, if a subject has multiple events occurring in the same SOC or same PT, the event with the highest association (i.e. related) to study drug will be summarized.

Adverse events will be presented in Internationally Agreed Order at SOC level and within each SOC, in decreasing order of the incidences (in MP-513, then in Placebo) at the PT level.

An overall summary of adverse events will be presented and will include:

- Subjects with at least one TEAE
- Subjects with any severe TEAE
- Subjects with any serious TEAE
- Subjects with any ADRs
- Subjects with any serious ADRs
- Subjects with any treatment emergent cardiovascular events
- Subjects with any study drug related treatment emergent cardiovascular events
- Subjects with any TEAE resulting in death
- Subjects with any ADR resulting in death
- Subjects with any TEAE leading to drug discontinuation
- Subjects with any ADR leading to drug discontinuation
- Subjects with Hypoglycaemia
- Subjects with study drug related Hypoglycaemia

The following summary tables will be presented by SOC and PT:

- All TEAEs
- TEAEs by relationship to study drug
- TEAEs by severity grade
- Serious TEAEs
- Treatment emergent cardiovascular events

- Study drug related treatment emergent cardiovascular events
- All ADRs
- Serious ADRs
- TEAEs leading to drug discontinuation,
- ADRs leading to drug discontinuation

The following listings will be presented by subject:

- All AEs
- TEAEs
- Serious TEAEs
- TEAEs leading to drug discontinuation
- Treatment emergent cardiovascular events
- All ADRs
- All hypoglycaemic episodes

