6.3.3 Withdrawals and Replacement of Subjects

Subjects may be discontinued from study at any time. Subjects are also free to discontinue their participation in the study at any time without prejudice to further treatment.

In the eCRF, study completion or discontinuation will be documented with the reason for any discontinuation. Possible reasons for a subject discontinuing participation in the study are:

- AE(s) that endanger the health of subjects, making it ethically unacceptable to continue

- Deterioration of the subject's clinical condition(s) that requires appropriate therapy/treatment during the study period
- Withdrawal of consent
- Other cases where the investigator decides the study for the relevant subject should be discontinued.

Subjects' condition are clearly no longer suitable to continue in the study. The subjects with a lack of glycaemic control during the double-blind treatment period will be discontinued from the study and referred to appropriate anti-hyperglycaemic therapy. Inadequate FPG measured in the central laboratory is defined as follows:

- (1) FPG > 270 mg/dL (15 mmol/L) from baseline to Week 8 (inclusive).
- (2) FPG > 240 mg/dL (13.3 mmol/L) from Week 8 to Week 12 (inclusive).
- (3) FPG > 200 mg/dL (11.1 mmol/L) from Week 12 to Week 24 (exclusive).

In case of an AE, the subject should be followed up, whenever possible, until the subject recovers or until the investigator considers the situation to be no longer clinically significant. Subjects who discontinue prematurely from the study will not be replaced.

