8.6 Extent of Exposure and Compliance to Study Treatment

Extent of Exposure and Compliance to Study Treatment will be summarized using the FAS, PPS and safety populations.

Duration of study drug exposure during the double blind treatment period and treatment compliance during the double blind treatment period will be calculated as mentioned in [section 6.6](#) and will be summarized descriptively.

The treatment compliance during double blind period will also be summarized for compliance $\leq 75\%$ and $>75\%$ using frequency counts and percentages.

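### SAP 8.8.1 tabulates adverse events and hypoglycaemia only as subjects with at least one event: follow-up time is ignored, and the number and category of hypoglycaemic episodes appear only in a listing

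*SAP*

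**What the plan says.** **Counting rule.** SAP 8.8.1 states: "A subject will only be counted once per SOC and PT within a treatment". Each line of its overall summary is a number of subjects. Hypoglycaemia has two such lines, "Subjects with Hypoglycaemia" and a second for drug-related cases. SAP 6.8.1 codes all episodes to one MedDRA term, so in the tables by SOC and PT a subject's repeat episodes also collapse to one count. All episodes go into a subject listing.

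**Inference.** SAP 8.8 states: "No formal statistical test would be performed to determine statistical significance between treatment groups". SAP 7.1 attaches confidence intervals to statistical tests, so the text plans none for a difference in event frequency.

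**Follow-up.** Protocol 6.3.3 states: "The subjects with a lack of glycaemic control during the double-blind treatment period will be discontinued from the study". The fasting glucose limits are 270, then 240, then 200 mg/dL, tightening after Weeks 8 and 12. The notes to the visit schedule (Protocol 6.6.1) end event collection 14 days after the final dose. The TEAE definition in SAP 6.8.1.1 starts on Day 1 and gives no end.

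**Exposure.** SAP 8.6 summarises "Duration of study drug exposure during the double blind treatment period", but no event summary uses it as a denominator.

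**Endpoint.** Protocol 6.9.1.6 lists hypoglycaemic episodes as a safety endpoint. Protocol 6.6.2.4 has the investigator classify each one as severe, documented symptomatic, asymptomatic, probable symptomatic or relative, with times, glucose value and other details.

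**The concern.** There are two separate issues.

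First, a crude percentage compares the arms fairly only if they are observed for about the same time. Here a subject can be removed because of poor glycaemic control, which treatment is meant to change. Protocol section 4 reports placebo-subtracted HbA1c reductions of 0.48 to 1.00 points at 20 mg in earlier trials, so more such exits on placebo is the natural expectation. The placebo arm would then have less time in which to record an event. Unlike chance, that distortion does not shrink with more subjects.

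Second, and whatever the dropout, an arm with one episode per affected subject and an arm with ten look the same in the tables. Protocol section 4 presents the drug as carrying no risk of hypoglycaemia. Episode frequency and category by arm are what a reader needs to examine that statement, and the SAP text leaves both to a listing.

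**Working it through.** **Inputs from the documents.** The planned size is "240 subjects (120 subjects to MP-513 and 120 subjects to placebo", and 120 + 120 = 240 agrees with 1:1 allocation. Treatment lasts 24 weeks and event collection runs 14 days past the last dose, so a completer is at risk for 24 + 2 = 26 weeks. The documents state no safety figure to reproduce, and the sample-size inputs are redacted.

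**Assumptions (not in the documents).**
- Withdrawal on MP-513 v placebo: 2 v 5%, 2 v 10%, 3 v 15%, 5 v 20% and 5 v 30%.
- Withdrawals spread evenly over Weeks 4, 8, 12, 16 and 20, each followed by 2 more weeks of collection.
- The same constant hazard in both arms, with a 26-week risk *p* from 2% to 70%. The only placebo AE incidence given is 46.5% over 12 weeks, in the thiazolidinedione combination study (Protocol section 4). At a constant hazard that is 1 − (1 − 0.465)^(26/12) = 74% over 26 weeks, so the upper end of the range is relevant.

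**Formulas.**
- Weekly hazard: λ = −ln(1 − p)/26.
- Mean risk in subjects who leave: m = average of 1 − exp(−λ(t + 2)) over the five exit weeks.
- Crude risk in an arm with withdrawal proportion d: (1 − d)p + d·m.
- Spurious difference: (d_placebo − d_MP-513)(p − m).
- 95% half-width with 120 per arm: 1.96·√(2p(1 − p)/120).

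**Example, p = 50%.** λ = 0.6931/26 = 0.02666. The five leaver risks are 0.148, 0.234, 0.312, 0.381 and 0.444, so m = 0.304. With 2 v 10% withdrawal, the crude risk is 0.98 × 0.50 + 0.02 × 0.304 = 49.6% on MP-513 and 0.90 × 0.50 + 0.10 × 0.304 = 48.0% on placebo. The excess is 1.6 points although the hazards are identical. With 5 v 30% it is 0.25 × (0.50 − 0.304) = 4.9 points.

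**Spurious excess on MP-513, in percentage points.**

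| 26-week risk | 2 v 5% | 2 v 10% | 3 v 15% | 5 v 20% | 5 v 30% | 95% half-width |
|---|---|---|---|---|---|---|
| 2% | 0.03 | 0.07 | 0.11 | 0.14 | 0.23 | 3.5 |
| 10% | 0.14 | 0.36 | 0.54 | 0.68 | 1.13 | 7.6 |
| 30% | 0.38 | 1.02 | 1.53 | 1.92 | 3.19 | 11.6 |
| 50% | 0.59 | 1.57 | 2.36 | 2.95 | 4.91 | 12.7 |
| 70% | 0.72 | 1.93 | 2.89 | 3.62 | 6.03 | 11.6 |

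Mean follow-up is 26 − 12d weeks: 25.8 v 25.4 for 2 v 5%, and 25.4 v 22.4 for 5 v 30%. At 2% risk the largest excess is 0.0023 × 120 = 0.28 of a subject.

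**Sensitivity to timing** (5 v 30% withdrawal, 50% risk). With all exits at Weeks 4 and 8 the excess is 7.7 points; with all at Weeks 12 to 20 it is 3.0. Both are below the 12.7-point half-width.

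**Effect of using time at risk.** With a constant hazard, expected first events divided by expected time at risk equals λ in either arm. At p = 50% that is 0.02666 × 52 × 100 = 138.6 per 100 subject-years in both, a ratio of 1.00 whatever the withdrawal pattern.

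**Episodes.** No arithmetic is needed. The protocol names episodes as the endpoint and records them singly by category; SAP 8.8.1 tabulates subjects and lists episodes.

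**The case against.** The strongest reply is that the distortion is small, conditional and visible. The documents give no withdrawal rate by arm, so every figure above reflects chosen inputs. The shift is below sampling noise in every case run. No safety test depends on it, it runs against MP-513 and so would not hide harm, and the exposure table lets a reader see an imbalance. All of that stands, although an exposure table alone does not let a reader correct each event percentage.

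A reader might infer that equal risks will show as an excess of hypoglycaemia on MP-513. The documents do not support that. The placebo time lost comes from subjects with high fasting glucose, whose hypoglycaemia risk is plausibly low. Protocol 6.5.1 lets subjects withdrawn for lack of control use other anti-diabetic drugs after the early termination visit, possibly inside the 14-day collection period, and the TEAE definition has no end. Such episodes would be attributed to placebo, so the direction could reverse.

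A reader might also infer that repeat hypoglycaemia is not captured. It is: every episode is recorded and listed. What the SAP text lacks is tabulation, and even that is subject to a check, because the table shells in SAP section 12 are in the contents list but were not available. They may hold an event-count column.

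Finally, person-time rates are not neutral. If events cluster early, a rate is diluted in the arm followed longer, which would favour MP-513. This also stands, and is why the rates should supplement the crude percentages.

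**Conclusion.** The point holds as a modest improvement to the safety tables. As written, SAP 8.8.1 uses only crude subject counts. If more placebo subjects leave under the glucose limits, and hazards are equal and constant, the crude TEAE percentage would be expected to be higher on MP-513 by about 0.6 to 5 points at 50% risk and by under 0.3 points at 2% risk. These sizes rest on assumed withdrawal rates and evenly spread exits. They do not establish that a distortion will occur, and for hypoglycaemia even its direction is open.

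The episode issue is firmer because it needs no dropout assumption: the SAP text does not tabulate the frequency or category of a named endpoint by arm. The only reservation is the table shells that could not be checked.

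**What to change.** Keep the crude tables. In SAP 8.8.1 add:

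1. The number of hypoglycaemic episodes, and episodes per 100 subject-years, by arm and by the five categories of Protocol 6.6.2.4.
2. For any TEAE, serious TEAEs, ADRs, cardiovascular events and hypoglycaemia, the number of subjects with a first event per 100 subject-years at risk by arm, with the rate difference and its 95% confidence interval, and no test.

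For the first-event rates, define time at risk as Day 1 to the first event or 14 days after the last dose, whichever is earlier. For the episode rates, continue time to 14 days after the last dose, since a subject remains at risk of further episodes. End the TEAE window at the same point. Do not use the exposure duration of SAP 6.6 as the denominator: it runs from randomization to Visit 6, or to tablet return after early withdrawal, so it omits the 14-day tail and does not stop at a first event.

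The data are already collected, and no visit, test or alpha is involved. The cost is a second set of rates to explain, and a rule for events with unknown start dates: SAP 7.3.1 can count these as TEAEs, but they have no time of onset. The rates also assume a roughly constant hazard, so the tables should say that they are to be read beside the crude percentages.
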